## 13. ADVERSE EVENT REPORTING

**13.1. Adverse Events**

At each evaluation, the investigator will determine whether any adverse events (AEs) have occurred, whether expected or not. Adverse events occurring between required study visits will be recorded on the case report form of the next required visit. For the purpose of this protocol, an adverse event is any untoward medical occurrence in a subject. All AEs occurring during the trial period will be recorded in the case report form.

*13.1.1. Adverse Event Severity*

For the trial, the Investigators will categorize and report the severity of adverse events as follows:

- **Mild** = The AE is transient and easily tolerated by the subject.
- **Moderate** = The AE causes the subject discomfort and interrupts the subject's normal activities.
- **Severe** = The AE:
  - is life threatening;
  - results in permanent impairment of a body function or permanent damage to a body structure;
  - necessitates medical or surgical intervention to preclude permanent impairment of a body function or permanent damage to a body structure; or
  - results in hospitalization or prolongation of hospitalization.

*13.1.2. Adverse Event Relatedness*

The Investigators will also categorize and report the relatedness of the AEs as follows:

- **Systemic** = adverse events that are not related to the target breast (e.g. pulmonary embolus, allergic reactions to general anesthesia, illness, etc.)
- **Related to Target Breast** = adverse events that occur in or around the target breast that cannot be directly attributed to the implanted Meso BioMatrix (e.g. hematoma, pain, etc.).

- **Related to Investigational Device** = adverse events that may be directly linked to the implanted Meso BioMatrix.
- **Related to Prosthesis** = adverse events that may be directly linked to the tissue expander or breast implant.

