#### **9.4. Risks Associated with Biologic Surgical Mesh**

The potential risks and benefits of participation in this trial are described in the subject informed consent form and are to be explained to the subject and/or their legal representative prior to participating in the trial.

The potential complications associated with the use of biologic surgical mesh during breast reconstruction are listed below. These complications are therefore also possible with the use of Meso BioMatrix during breast reconstruction. However, there may be unforeseen additional risks. The potential investigational device related complications are:

- Infection;
- Seroma;
- Hematoma;
- Tissue necrosis;
- Dehiscence;
- Erythema;
- Local or systemic allergic reaction to the Meso BioMatrix implant; and
- Defect Recurrence.

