## **11. STATISTICAL CONSIDERATIONS**

### **11.1. Sample Size Justification**

This is a feasibility trial with no formal statistical hypothesis. Therefore, the sample size of 25 subjects was empirically chosen.

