#### **11.4. Criteria for Trial Termination**

All serious adverse events and unanticipated adverse device effects reported during the trial will be evaluated to determine if the investigational device poses an unacceptable risk to subjects. If an unacceptable risk is determined in the judgment of the Investigators, the sponsor and/or the U.S. Food & Drug Administration, enrollment in the trial will be suspended while an

investigation into the cause of the unacceptable risk is undertaken. If the unacceptable risk cannot be mitigated by modifications to the investigational device or the investigational plan, the trial will be terminated.

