#### *11.4.1. Stopping Rules Related to the Investigational Device*

DSM Biomedical will follow the below formal stopping rules in order to assure that enrollment will be suspended in a timely manner should potential serious safety issues arise unique to the investigational device:

- A serious immune reaction requiring surgical revision/removal of the investigational device occurs in 2 subjects.
- An investigational device malfunction requiring post-operative surgical revision/removal of the investigational device occurs in 3 subjects.
- A serious adverse event potentially related to the investigational device occurs in 5 subjects.
- A serious unanticipated adverse device effect is determined to have occurred.

Should one of the above stopping criteria occur, DSM Biomedical shall suspend enrollment as soon as possible, but not later than 5 working days after the determination that a stopping rule criterion has been met. The trial will remain suspended until the FDA and the each IRB have approved trial resumption.

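### Hematoma is the relatedness scale's example of a non-mesh event but a listed mesh complication in 9.4, and nothing ties the scale to the five-subject stopping rule

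*Combined protocol and SAP*

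**What the plan says.** Section 13.1.2 gives the coding task to the surgeons: "The Investigators will also categorize and report the relatedness of the AEs as follows". Four categories follow: systemic, target breast, investigational device and prosthesis. The target-breast category takes events in or around that breast that "cannot be directly attributed to the implanted Meso BioMatrix (e.g. hematoma, pain, etc".). The device category takes "adverse events that may be directly linked to the implanted Meso BioMatrix".

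Section 9.4 introduces its list for biologic mesh with "The potential investigational device related complications are". Hematoma is on that list, with infection, seroma, tissue necrosis, dehiscence, erythema, allergic reaction and defect recurrence.

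Section 11.4.1 has four triggers for suspending enrollment. The third is: "A serious adverse event potentially related to the investigational device occurs in 5 subjects". The first two concern serious immune reactions and device malfunctions that need surgical revision or removal, and the fourth concerns serious unanticipated device effects. The third is therefore the only trigger that puts a number on the ordinary complications in 9.4.

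Outside the count, 11.4 provides that "All serious adverse events and unanticipated adverse device effects reported during the trial will be evaluated".

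**The concern.** The coding scale and the risk section point in different directions for the same event. A surgeon who follows the example in 13.1.2 files a hematoma under the target breast, although 9.4 treats hematoma as a possible consequence of the mesh.

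The stopping rule then turns on a possible relationship to the device. Section 13.1.2 does not use that term, and no section maps its four categories onto the rule. A serious infection, seroma or necrosis of uncertain cause can satisfy both the target-breast and the device definition, so two investigators could code the same event differently and both comply with the protocol.

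At stake is whether the trigger works as worded. With a threshold of five subjects, one or two uncounted subjects can decide whether enrollment is suspended.

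**Working it through.** **Comparison of the sections**

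| Section | Treatment of hematoma | Treatment of uncertain cause |
|---|---|---|
| 9.4 | Listed as a possible mesh complication | A list of possibilities; no coding rule |
| 13.1.2, target breast | Named example | Takes events that lack a direct attribution to the mesh |
| 13.1.2, device | Not named | Takes events that might have a direct link to the mesh |
| 11.4.1, third rule | Not named | Counts serious events with a potential relationship to the mesh |

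An event that might be linked to the mesh but for which no direct attribution can be made meets both middle definitions. Hematoma is the only 9.4 complication that the scale names on the non-device side. For the others, omission depends on how the investigator reads the boundary.

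**Illustration of size**

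The protocol gives no operating characteristic for the rule, so there is no figure to reproduce. Section 11.1 says "This is a feasibility trial with no formal statistical hypothesis" and that "the sample size of 25 subjects was empirically chosen".

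Inputs from the protocol:
- 25 subjects (5.9, 11.1) and a threshold of 5 subjects (11.4.1). 5/25 = 20%.
- Hematoma in Table 1 (4.2): 0 to 6.7% in one review and 1.4% in another. These are rates of any severity, per implant.

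Assumptions:
- The true per-subject rate *p* of serious events potentially related to the mesh is 30%. The protocol gives no such rate.
- Subjects are independent, and all 25 contribute.
- The Table 1 hematoma rate *h* is used as a serious, per-subject rate, and a subject with a hematoma has no other counted event. Leaving hematoma out then reduces the counted rate to *p* − *h*.

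Formula: P(X ≥ 5) = 1 − Σ(k = 0 to 4) C(25, k) q^k (1 − q)^(25 − k), where q is the counted rate.

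| Hematoma rate left out | q | P(X ≤ 4) | P(rule met) |
|---|---|---|---|
| 0% (nothing lost) | 0.300 | 0.0905 | 0.91 |
| 1.4% | 0.300 − 0.014 = 0.286 | 0.1172 | 0.88 |
| 6.7% | 0.300 − 0.067 = 0.233 | 0.2748 | 0.73 |

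Sensitivity to the assumed true rate:

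| True rate | All counted | Hematoma out at 1.4% | Hematoma out at 6.7% |
|---|---|---|---|
| 10% | 0.098 | 0.059 | 0.001 |
| 15% | 0.318 | 0.247 | 0.052 |
| 20% | 0.579 | 0.509 | 0.232 |
| 25% | 0.786 | 0.737 | 0.493 |
| 30% | 0.910 | 0.883 | 0.725 |

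Expected number of subjects with hematoma: 25 × 0.014 = 0.35 and 25 × 0.067 = 1.7.

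Two features make these figures illustrative only. Serious hematoma per subject is probably rarer than hematoma of any severity per implant, so the loss is probably overstated. The rule also only suspends enrollment, so an event after the last enrollment cannot be acted on through it, whereas the calculation uses all 25 subjects.

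**The case against.** The case against has four parts.

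1. **The scale does admit possibility.** The device category is worded as events that may have a direct link, so a reader who infers that the scale has no place for a possible relationship goes too far. This stands. The defect is an unclear boundary and a missing mapping.
2. **The rule need not read the code.** Section 11.4.1 does not say that the count is taken from the 13.1.2 category, and 13.1.2 does not say that only one category may be chosen. The sponsor could count a serious hematoma coded to the target breast on the strength of the rule's own wording. This also stands: the protocol shows that events can be omitted, not that they will be. It equally shows that nothing says who counts, or from what.
3. **The two sections can coexist.** Section 9.4 lists what can happen with biologic mesh, while 13.1.2 classifies individual events. Hematoma is also listed as a risk of the expander (9.2) and of the breast implant (9.3), so a given hematoma may have nothing to do with the mesh. That is true of single cases. It does not justify naming hematoma as the standard example of a non-mesh event.
4. **Safety review does not depend on the code.** All serious events go to the sponsor and the IRB within 48 hours (13.2), are evaluated under 11.4, and fall under the sponsor's duty in 14.3.10 to suspend enrollment if event rates are significantly raised. A reader might infer that miscoded events escape safety control; the protocol does not support that. These backstops are matters of judgment without a number, however, and 11.4.1 was added as a formal rule to secure timely suspension.

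A reader might also infer a much larger loss. If only half of all qualifying events were coded to the device, the chance at a 30% true rate would fall from 0.91 to 0.32 (q = 0.15). No section supports that fraction, and it would require many events other than hematoma to be coded away.

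**Conclusion.** The point holds in limited form. Sections 9.4 and 13.1.2 conflict on hematoma, the boundary between the target-breast and device categories is ambiguous, and no section connects them to the third stopping rule. A qualifying serious event can therefore drop out of that count, though not out of expedited reporting or general safety review.

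For hematoma alone the effect runs from none to moderate: 0.91 to 0.88 or 0.73 under the stated assumptions, and unchanged if no serious hematoma occurs. A larger loss needs other breast events of uncertain cause to be coded away as well, and the protocol gives no basis for putting a number on that. The need for a correction rests on the conflict in the text rather than on these probabilities.

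**What to change.** Reconcile 9.4, 11.4.1 and 13.1.2:

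- Remove hematoma as the example of a non-device event in 13.1.2.
- For every serious breast event, record whether a relationship to the mesh is possible, even when another category also applies.
- State in 11.4.1 that the third rule counts every serious event for which such a relationship is possible, which is what its present wording already implies, and name who makes that determination.

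Separate fields for the prosthesis and the biopsy are not needed for this point.

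The cost is protocol wording and one case report form item. The downside is that the rule may be reached earlier or more often, and each trigger suspends enrollment until the FDA and the IRBs approve resumption.

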#### 13.1.3. *Immediate Post-operative Symptoms as Adverse Events*

Subjects in this trial will undergo two, possibly three, breast related surgeries. Pain, redness and swelling at the surgical site will occur in every subject following each surgery. Therefore, immediate post-operative symptoms and function restrictions will only be categorized as adverse events when a subject's complaint for any of these symptoms results in an unscheduled visit or when a subject presents with new or worsening symptoms as compared to the previous visit.

#### 13.2. **Serious Adverse Events**

Serious adverse events (“SAEs”) in this trial are adverse events that meet the definition of severe in section 13.1. All SAEs will be documented on the case report form. Investigators must also report SAEs to DSM Biomedical and the relevant Institutional Review Board within 48 hours of learning of the SAE. The Investigator shall make such notification to the sponsor on a Report of Serious Adverse Event in the case report form.

#### 13.3. **Unanticipated Adverse Device Effects**

An unanticipated adverse device effect (“UADE”) is defined as either:

- any serious adverse effect on health or safety or any life-threatening problem or death caused by, or associated with, a device, if that effect, problem, or death was not previously identified in nature, severity, or degree of incidence in the investigational plan; or
- any other unanticipated serious problems associated with a device that relates to the rights, safety, or welfare of subjects.

Investigators must report UADEs to DSM Biomedical and the relevant Institutional Review Board within 48 hours of learning of the UADE. The Investigator shall make such notification on a Report of Serious Adverse Event form and document the UADE on the case report form. Following the report of the UADE, DSM will immediately conduct an investigation to determine the cause of the UADE and assess the level of risk to current and potential future research subjects. DSM will report the results of UADE evaluations, including any identified corrective actions, to FDA, all reviewing IRBs and all participating investigators within 10 working days after DSM first receives notice of the UADE. If DSM determines that the UADE presents an unreasonable risk to subjects based on a risk analysis, DSM shall terminate enrollment as soon as possible, but not later than 5 working days after this determination and not later than 15 working days after DSM first received notice of the UADE.

### 14. TRIAL RESPONSIBILITIES

#### 14.1. **General Responsibilities**

##### 14.1.1. *Subject Confidentiality*

Subject confidentiality is of utmost importance to all parties involved in this trial. DSM Biomedical, the Investigators, all assisting contract research organizations, monitors and the Core Lab will take appropriate steps to protect the identity of research subjects as stated in the HIPAA law.

##### 14.1.2. *Good Clinical Practice Guidelines*

DSM Biomedical, the Investigators, all assisting contract research organizations, monitors and the Imaging Core Lab will follow Good Clinical Practice Guidelines (GCP) in the conduct of this trial.

#### 14.2. **Investigator Responsibilities**

The investigator is responsible for ensuring the investigation is conducted according to all signed agreements and the Investigational Plan. This section further describes each Investigator's responsibilities.

**14.2.1. Institutional Review Board (IRB) Approval**

The investigator must submit the trial protocol to his/her IRB and obtain their written approval before being allowed to enroll subjects in the trial. The investigator is also responsible for fulfilling any conditions of approval imposed by the IRB, such as regular reporting, reporting of SAEs, etc.

**14.2.2. Informed Consent Form**

Part of the IRB approval must include approval of the Informed Consent Form specific to this trial. The investigator must administer the approved Informed Consent Form to each prospective trial subject, and obtain the subject's signature on the on the Informed Consent Form, prior to enrollment in the trial. The sample Informed Consent is included in section 7 of the Investigational Plan. The sample Informed Consent Form may be modified to suit the requirements of the individual site and IRB.

**14.2.3. Protocol Compliance**

Investigators must not deviate from the protocol. The only allowable exceptions are in cases of emergency to protect subject safety. All deviations from the protocol must be recorded in the case report form along with an explanation for the deviation. Continued deviations from the protocol may lead to termination of the investigator's participation in the trial.

**14.2.4. Records**

Each investigator must maintain current, precise and safeguarded records relating to the conduct of the investigation kept in a locked and restricted access area. These records include:

- correspondence with the IRB and the Sponsor,
- records of receipt, use and disposition of trial devices,
- records of each subject's trial participation.

Each investigator must retain the records of the investigation for at least 2 years after the completion of the trial or 2 years after the approval of a marketing application in the United States, whichever occurs last.

**14.2.5. Reports**

Investigators are responsible for reports of serious adverse events, unanticipated device effects, withdrawal of IRB approval, deviations from the investigational plan, use of the device without consent, progress reports and final reports. These reports must be submitted to the IRB and copies must be submitted to the Sponsor. Investigators must report serious adverse events and unanticipated adverse device effects to the sponsor with 48 hours of learning of the event.

**14.3. Sponsor Responsibilities**

DSM Biomedical is the sponsor of the trial. DSM Biomedical's responsibilities in the trial include:

**14.3.1. Quality Assurance and Quality Control**

Implement and maintain quality assurance and quality control to ensure the trial is conducted according to the Investigational Plan and applicable laws and regulations.

**14.3.2. Investigational Plan Approval**

Provide the Investigational Plan to the applicable regulatory authorities and to the Investigators. DSM Biomedical will ensure the Investigational Plan is approved by the applicable Institutional Review Board at each site prior to first subject enrollment.

*14.3.3. Ensure Compliance with Investigational Plan and Regulations*

DSM Biomedical will ensure the Investigators and all contracted parties comply with the Investigational Plan and all applicable regulations. If non-compliance is identified, DSM Biomedical shall take prompt and appropriate action to secure compliance or terminate the Investigator's or contracted party's participation in the trial.

*14.3.4. Device Supply and Accountability*

Provide properly labeled and packaged investigational devices to the participating trial sites in a quantity sufficient to support trial activities. DSM Biomedical will maintain a master record of all supplied, used, returned and destroyed investigational devices.

*14.3.5. Device Training*

Provide investigational device training to Investigators and trial site staff.

*14.3.6. Investigator Selection*

Select the Principal Investigator, all clinical investigators at the trial sites, and any consultants who participate in the trial. Eligible Investigators are those who are experienced in the treatment of the target population and who agree to allow direct access to trial records for the purpose of monitoring and auditing trial data.

*14.3.7. Financial Support*

Provide financial support at fair market value to the Investigators and/or personnel at the trial site in order to adequately conduct the trial.

*14.3.8. Establish Regulatory Standards*

Establish the regulatory standards to be followed for the clinical trial and other participants. All trial participants shall follow GCPs.

*14.3.9. Monitoring Oversight*

Assure site monitoring is performed in compliance with applicable regulations.

*14.3.10. Safety Oversight*

Monitor the safety of the use of the investigational device on an ongoing basis. If a significantly greater rate of SAEs or other adverse events are observed, it is the sponsor's responsibility to suspend enrollment in the trial to prevent subjects from being exposed to unnecessary risks while the root cause is being determined. DSM Biomedical shall promptly inform the Principal Investigator and the Site Principal Investigators about any UADEs occurring during the trial. Such notification shall be sent in writing.

*14.3.11. Trial Reports*

Provide annual progress reports and the final trial report to the Investigators and applicable regulatory authorities.

*14.3.12. Trial Registration*

Register the trial on the clinicaltrials.gov website if required in Title VIII of the Food and Drug Administration Amendments Act of 2007.

**14.4. Monitor Responsibilities**

The monitors are responsible for the following:

*14.4.1. Ensuring Compliance with the Investigational Plan and Applicable Regulations*

Ensure the rights, safety and welfare of trial subjects are being protected as required by the Investigational Plan and applicable regulations. Ensure the Investigators are complying with the procedures in the Investigational Plan. Ensure the Investigators are properly protecting and accounting for investigational devices. The monitor will also determine if the Investigator is maintaining the necessary regulatory documents.

#### 14.4.2. Verifying Trial Data

Verify data on the case report form against the source documents for completeness and accuracy. Inform the Investigator and/or Research Coordinator of any discrepancies between the data on the case report form and the source documents and ensure appropriate corrections are made. Ensure all protocol deviations and adverse events are properly reported on the case report form.

### 15. PUBLICATION POLICY

DSM Biomedical retains ownership of all clinical data generated in this trial, and controls the use of the data for purposes of regulatory submissions. DSM Biomedical will exercise no veto over publication of trial results in the medical literature but must be provided with advance copies of manuscripts and abstracts to review for technical accuracy and confidential information. However, the Principal Investigator for the trial shall have first right of publication. No individual site experiences may be published prior to the principal trial manuscript without the expressed consent of the Principal Investigator and DSM Biomedical.

